Antimicrobial resistance is one of the largest threats to global health, stated by The World Health Organization (WHO)¹. Antibiotic use is the main driver of selection of resistant bacteria², and resistance develops quickly after any antibiotic use. Primary health care is responsible for 90% of all antibiotic prescriptions in human in Denmark³. General practitioners (GPs) issue 75% of these prescriptions⁴ with acute lower respiratory tract infections (LRTIs) being one of the most common indications⁵.

Acute LRTIs includes several different conditions with overlapping symptoms such as acute bronchitis and community-acquired pneumonia (CAP)⁶. No single symptom or specific point of care test (POCT) cut-off value, e.g. C-reactive protein (CRP), can be used to discriminate the diagnoses^{7,8}. It is well known that this diagnostic uncertainty leads to overuse of antibiotics⁹.

An alternative mode of diagnosing CAP is using focused lung ultrasound FLUS. Several studies have demonstrated that FLUS has an excellent accuracy for diagnosing pneumonia in hospitalised adults¹⁰⁻¹⁵. FLUS is not a common application for GPs using point-of-care ultrasonography (POCUS)¹⁶ in general practice, even though GPs are increasingly using POCUS¹⁷. We do not know yet if FLUS can help discriminating between benign self-limiting acute LRTIs and bacterial CAP in general practice. **This trial aims to pragmatically determine if the addition of FLUS to usual care can effectively reduce the prescription of antibiotics** in patients presenting to general practice with an acute LRTI.

2. Study Objectives, Hypothesis and Outcomes

2.1. Primary Objective and Outcome

Primary objective: To determine if adding focused lung ultrasonography (FLUS) to usual care of patients presenting with symptoms of an acute lower respiratory tract infection (LRTI) in general practice reduces the general practitioner's (GP) antibiotic prescribing at index consultation (day 0).

The primary outcome: The proportion of participants who are prescribed antibiotics during index consultation (day 0).

The null hypothesis is that there is no difference in the proportion of participants who are prescribed antibiotics during index consultation in participants who have FLUS performed in addition to usual care compared to those who receive usual care only.

The alternative hypothesis is that FLUS, performed by the GP in addition to usual care, will lead to a significant decrease in the proportion of participants who have antibiotics prescribed during index consultation.

2.2. Secondary Objectives and Outcomes

Secondary objectives:

- To compare the clinical course of participants in terms of antibiotics prescribed up to day 28, duration and burden of LRTI symptoms, re-consultations, imaging performed, illness deterioration (hospitalization, complications, all-cause mortality), referral for and number of cancer diagnoses in review of medical records up to day 60, and spontaneously reported unintended events detected up to day 60.
- To assess participants' satisfaction with the index consultation.

Secondary outcomes:

1) Outcomes from the LRTI symptom diary:

Participants will be asked to complete a validated LRTI symptom diary every day from the day of index consultation (day 0) to day 21¹⁸. The recorded items include the following six symptoms of LRTI: cough, dyspnea, sputum production, well-being, sleep disturbance, and activity disturbance. The participants are asked to consider how bad each symptom has been over the past 24 hours by scoring each symptom on a 7-point Likert scale (0 = no problem, 1 = very little problem, 2 = slight problem, 3 = moderate problem, 4 = bad problem, 5 = very bad problem, and 6 = as bad as it could be). Moreover, the diary contains a social domain on cancellation of work-related or leisure activities. Only on the day of the index consultation (day 0) the diary will incorporate a question on participants' satisfaction with the consultation assessed on a 5-point Likert scale (very dissatisfied (1) to very satisfied (5)).

- 1.1) Daily total LRTI symptom score, calculated as the sum of the scores for six symptoms
(minimum 0 – maximum 36) (mean/median).
- 1.2) The number of days with symptoms rated as “moderate problem” or worse by the participant (at least one item with a score of 3 or above) (mean/median).
- 1.3) Number of days participants signed in sick/cancelled work-related activities or cancelled leisure activities (mean/median).

- 1.4) Proportion of participants who were satisfied or very satisfied (4 or 5) with the index consultation.

Outcomes 1.1, 1.2 and 1.3 from the LRTI symptom diary will be calculated for each participant every day from day 0 until the participant has scored 0 for every item, whichever comes first, or up to a maximum of 21 days.

2) Outcomes from participants' shared medication records (i.e., FMK) and on type of prescription:

As standard care and communication method, data on changes in medicine or new prescriptions are automatically uploaded to participants' electronic shared medication record (FMK). We will review the participants' shared medication records (FMK) for outcomes on antibiotics prescribed during follow-up:

- 2.1) Proportion of participants who have antibiotics prescribed within 7 days after the index consultation.
- 2.2) Proportion of participants who have antibiotics prescribed within 28 days after the index consultation.
- 2.3) Proportion of antibiotics prescribed as delayed antibiotic prescriptions at index consultation (day 0).

As standard care and communication, GPs receive notices of health-related events, e.g., discharge and out-of-hour notices. From participants' electronic medical records, we will obtain outcomes on the clinical course during follow-up:

3) Outcomes from participants' electronic medical records:

- 3.1) Proportion of participants with reconsultations, defined as any primary care contact (general practice or out-of-hour services), within 28 days after the index consultation.
- 3.2) Proportion of participants admitted to the hospital within 28 days after the index consultation.

- 3.3) Proportion of participants with complications (pleural infection (defined as complicated parapneumonic effusion or empyema), lung abscess, or sepsis) during admission to hospital within 28 days after the index consultation.
- 3.4) Proportion of participants with imaging other than FLUS (any imaging performed in secondary health care services) performed within 28 days after the index consultation.
- 3.5) Other imaging methods performed within 28 days after the index consultation.
- 3.6) Proportion of participants referred with suspicion of cancer within 60 days after the index consultation.
- 3.7) Proportion of participants diagnosed with cancer within 60 days after the index consultation.
- 3.8) Number of spontaneously reported unintended events up to 60 days after the index consultation.
- 3.9) All-cause mortality up until day 28 and day 60.

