5.2. Lost to follow-up and missing data

In the case of missing data on the primary endpoint, the GP who enrolled the participant will be contacted to clarify if antibiotics were prescribed at the index consultation. If clarification is not obtained, we will consider it as if antibiotics were prescribed at the index consultation. We expect that the use of an e-CRF for GPs to complete at the time of index consultation will keep missing data on the primary outcome at a minimum. We expect that only observed data will be included in the secondary analyses.

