5.5. Secondary Outcomes

Table 1: All measured outcomes at different endpoints with type of data and planned statistical analyses are listed below

Outcome	Unit/options	Endpoint (days from index consultation)					Type of data	Statistical analyses
		0	0-21	7	28	60		
Secondary outcomes								
Daily total LRTI symptom score	0-36		X				Ordinal	Mean/Median, 95% CI, Chi ² or Fischer's exact
Duration of symptoms rated 3 or above	Days		X				Ratio	Mean/Median, 95% CI, Independent samples t-test/Mann Whitney U
Cancelled work related activities	Days		X				Ratio	Mean/Median, 95% CI, Independent samples t-test/Mann Whitney U
Cancelled leisure activities	Days		X				Ratio	Mean/Median, 95% CI, Independent samples t-test/Mann Whitney U
Satisfied or very satisfied (4 or 5) with index consultation	1 (very dissatisfied), 2 (dissatisfied), 3 (nor dissatisfied or satisfied), 4 (satisfied), 5 (very satisfied)	X					Nominal	Proportions, Chi ² or Fischer's exact
Type of antibiotic prescription at index consultation	Immediate/Delayed	X					Nominal	Proportion, RR, 95% CI, Chi ² or Fischer's exact
Antibiotic prescribed within 7 days after index consultation	Yes/No			X			Nominal	Proportion, RR, 95% CI, Chi ² or Fischer's exact
Antibiotic prescribed within 28 days after index consultation	Yes/No				X		Nominal	Proportion, RR, 95% CI, Chi ² or Fischer's exact
Reconsultation within 28 days after index consultation	Yes/No				X		Nominal	Proportion, RR, 95% CI, Chi ² or Fischer's exact
Hospitalization within 28 days after index consultation	Yes/No				X		Nominal	Proportion, RR, 95% CI, Chi ² or Fischer's exact
Complication within 28 days after index consultation	Yes/No				X		Nominal	Proportion, RR, 95% CI, Chi ² or Fischer's exact

Referred for suspicion of cancer (any) within 60 days after index consultation	Yes/No				X	Nominal	Proportion, RR, 95% CI, Chi ² or Fischer's exact
Diagnosed with cancer (any) within 60 days after index consultation	Yes/No				X	Nominal	Proportion, RR, 95% CI, Chi ² or Fischer's exact
All-cause mortality within 60 days after index consultation	Yes/No				X	Nominal	Proportion, RR, 95% CI, Chi ² or Fischer's exact
Adverse event within 60 days after index consultation	Yes/No				X	Nominal	Proportion, RR, 95% CI, Chi ² or Fischer's exact

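### The daily symptom score (outcome 1.1) stops at each participant's first all-zero day, with no rule for later days and no fixed unit of summary, so a literal analysis can compare groups formed after randomisation

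*SAP*

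**What the plan says.** The secondary objectives in SAP section 2.2 include comparing "duration and burden of LRTI symptoms". Outcome 1.1 is the "Daily total LRTI symptom score, calculated as the sum of the scores for six symptoms", with range 0 to 36 and a mean or median as summary. The sum runs over symptoms within one day, not over days.

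The same section asks participants to fill in the diary daily through day 21. It then limits what is computed: outcomes 1.1, 1.2 and 1.3 "will be calculated for each participant every day from day 0 until the participant has scored 0 for every item, whichever comes first". The calculation is capped at 21 days.

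Three other places bear on how this would be carried out:

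- Section 5.5, Table 1, has one row for "Daily total LRTI symptom score", ticked for days 0-21, with range 0-36, labelled ordinal. The analysis cell begins "Mean/Median, 95% CI, Chi ² or" and goes on to Fisher's exact test.
- Section 5.2: "We expect that only observed data will be included in the secondary analyses".
- Section 5.1 specifies intention to treat.

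No section says that days after the first all-zero day count as 0, or that scores recorded on those days are used.

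**The concern.** Recovery happens after randomisation, and the intervention may affect it. If a participant leaves the calculation on recovering, the set still contributing on a later day is selected by the course of illness. Where the arms recover at different speeds, those sets are no longer comparable, and a difference in their mean scores is not a difference in symptom burden between the groups as randomised.

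In a trial that aims to reduce antibiotic prescribing, symptom burden is one of the checks that patients are not worse off. A summary that can turn benefit into apparent harm, or the reverse, weakens that check. Because the unit of summary is open, the choice among analyses with different properties would be made at the analysis stage.

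**Working it through.** **Inputs.** The SAP has no figure to reproduce here: it gives no means, SDs or recovery times for the diary. Only the 195 participants per arm (section 3.3) come from the document. Everything else is assumed for illustration:

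- half the participants are mild (starting score 14, recovery about day 10) and half severe (22, about day 18);
- SD is 3 for starting score and 3 days for recovery;
- scores decline linearly to 0, are rounded to integers, and do not relapse;
- 400,000 simulated trajectories per arm.

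Differences are FLUS minus usual care, with simulation noise of about 0.02.

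**Reading (a): mean on each day.** Without relapse, a participant past the first all-zero day would add 0 to the mean over everyone. So, on any day,

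mean under the rule = mean over all participants / share still contributing.

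The rule divides each arm's mean by that arm's own share. Large effect, mild half recovering 3 days sooner under FLUS, day 10:

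- usual care: 5.33 / 0.79 = 6.7, with 0.79 x 195 = 154 contributing;
- FLUS: 4.85 / 0.61 = 8.0, with 0.61 x 195 = 119 contributing;
- difference over all participants: 4.85 - 5.33 = -0.48;
- difference under the rule: about +1.25 (7.98 - 6.73).

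Other assumed patterns:

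| Pattern under FLUS | Day | All participants | Under the rule |
|---|---|---|---|
| No recovery difference | 10 | +0.02 | +0.01 |
| Mild half 3 days later | 14 | +0.26 | -0.64 |
| Everyone 2 days sooner | 10 | -1.20 | -0.45 |
| Severe half 3 days sooner | 10 | -1.28 | -1.54 |
| 30% of mild cases 2 days sooner | 10 | -0.11 | +0.20 |

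The last row is scaled to the plan's own effect. Section 3.3 expects prescribing to fall by 15 percentage points. If all the changed participants are in the mild half, 15 / 50 = 30% of mild cases change. A 3-day average shift in the mild half would then need 3 / 0.30 = 10 days per changed participant, so the 3-day pattern is an upper-end case. At 195 per arm the standard error of the day-10 difference is about 0.5.

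**Reading (b): mean over each participant's calculated days.** The denominator is length of illness. A straight line from S to 0 averages about S/2 whatever its length, so under linear decline a pure shift in recovery nearly cancels. With the mild half 3 days sooner, 6.03 - 6.51 = -0.48 over fixed days 0-21 becomes 8.92 - 8.98 = -0.06. Other shapes behave differently:

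- scores 15% lower with unchanged recovery days: -0.85 becomes -1.12;
- a fast decline with a low tail until recovery, mild cases 3 days sooner: -0.11 becomes +0.53.

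So (b) is unreliable, but in no fixed direction.

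**Reading (c): sum over days 0-21 per participant.** Dropping zeros leaves a sum unchanged: 143.2 vs 132.6 with or without the rule. Only relapse matters. But such a sum could reach 22 x 36 = 792, which fits poorly with the stated range of 0-36.

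**The case against.** The best defence is that a benign reading exists. The sentence is written per participant and covers 1.1 together with 1.2 and 1.3, which are counts of days. Table 1 has one row for 1.1 rather than one per day, and the plan follows intention to treat. Someone who has scored 0 on every item has a known status, so carrying 0 forward is a natural completion. Under that completion, or under a per-participant sum, nothing is distorted apart from relapse. This stands as a possible intention, but the text does not state it. The observed-data sentence in section 5.2 points the other way when a participant stops recording after recovery, and the 0-36 range argues against the sum.

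A second objection concerns size, and it stands. The +1.25 comes from an effect that is large beside the plan's own prescribing difference. At a more modest effect the distortion is below one standard error.

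A reader might also infer that averaging over calculated days always wipes out a real difference. The document does not support that: it follows from the assumed straight-line decline and fails under other shapes.

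**Conclusion.** The point holds as a defect in a stated rule for one secondary outcome. The plan cuts off the calculation of 1.1 at recovery, gives no value to later days, and leaves the unit of summary open. Followed literally as a daily mean or median, it compares subsets formed after randomisation. The resulting contrast can be attenuated, exaggerated or reversed if recovery differs between arms.

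Its size in this trial is unknown. Under assumed inputs the day-10 difference moves from about -0.5 to +1.25 for a deliberately large effect, and from about -0.1 to +0.2 for a small one, against a standard error of about 0.5. There is no distortion if recovery does not differ.

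A reader might go further and conclude that the sponsor has chosen a biased analysis, or that the trial's symptom result will come out with the wrong sign. The document supports neither. It leaves several readings open, one of them harmless without relapse, and holds no data on recovery. Outcomes 1.2 and 1.3 lose only relapse days, and the primary outcome is untouched. The change should be made before analysis, for the sake of a fixed convention and unit rather than because a large distortion has been shown.

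**What to change.** Replace the calculation sentence in section 2.2 with:

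*Outcomes 1.1, 1.2 and 1.3 are calculated over days 0-21 for all randomised participants with diary data; after a first day with all six items scored 0, recorded entries are used where present and unrecorded days count as 0 (for 1.2 and 1.3, as no such day).*

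Then name one summary for 1.1 there and in Table 1, for example the per-participant mean over the fixed days 0-21, which keeps the 0-36 range.

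The cost is one sentence, one clause and about one line of code, made as a versioned revision under section 6. No new data are needed, because the diary already runs to day 21. The small downside is the assumption that symptoms do not return after recovery unless they are recorded.

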3.3. Sample Size

Based on previous audit projects in general practice in Denmark²⁰⁻²¹, a Danish study by Holm et al.⁹ and a Dutch study on reducing antibiotic prescribing in patients with LRTI²², we assume to detect a 15% decrease in antibiotic prescribing in patients with LRTI from 50% (usual care) to 35% (+FLUS). Using a 5% significance level and a power of 80% a total of 340 patients with 170 trial participants in each arm is needed. We assume withdrawal or discontinuation by a maximum of 10% of participants²². Furthermore, we increase the sample size by 5% to account for covariates in the analyses. Consequently, we plan to include a total of 390 trial participants (195 in each arm). Each GP is encouraged to include a minimum of 10 participants to account for the individual effect of FLUS on antibiotic prescribing at a GP level.

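### Delayed prescribing is compared between arms only among participants prescribed an antibiotic at day 0, a subset defined by the primary outcome, so its RR, CI and test are not a randomised comparison

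*SAP*

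**What the plan says.** Section 2.2 lists three prescribing outcomes in sequence. The first two are counted over participants: 2.1 is "Proportion of participants who have antibiotics prescribed within 7 days after the index consultation" and 2.2 is "Proportion of participants who have antibiotics prescribed within 28 days after the index consultation". The third changes its base: 2.3 is "Proportion of antibiotics prescribed as delayed antibiotic prescriptions at index consultation (day 0".

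In Table 1 (section 5.5) the matching row is "Type of antibiotic prescription at index consultation". Its options are "Immediate/Delayed", whereas the 7-day and 28-day prescribing rows are coded yes/no. The analysis column for the row begins "Proportion, RR, 95% CI" and adds a chi-squared or Fisher test.

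Section 2.1 gives the primary outcome as "The proportion of participants who are prescribed antibiotics during index consultation (day 0". Section 3.3 sizes the trial on a change in "antibiotic prescribing in patients with LRTI from 50% (usual care) to 35% (+FLUS".

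**The concern.** Read as written, outcome 2.3 takes as its denominator the participants who received a prescription at day 0. Membership of that group is the primary outcome, and the trial is built on the expectation that FLUS will change it. The participants still prescribed an antibiotic after FLUS need not resemble those prescribed under usual care, so randomisation no longer protects the comparison.

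The measure is also a ratio whose denominator moves with treatment. It can rise when delayed prescribing per randomised participant has not changed, and it can stay near 1 when delayed prescribing has fallen. A reader shown an RR with a CI and a p-value would take it as an effect of FLUS on delayed prescribing. That matters in a trial about antibiotic use, although only one secondary outcome is involved.

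**Working it through.** **Inputs from the SAP.** Prescribing 50% in usual care and 35% in +FLUS, 5% significance level, 80% power, 170 per arm needed and 195 per arm planned (section 3.3); 1:1 allocation (section 3.1).

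**Input not in the SAP.** The share of usual-care prescriptions that are delayed. I assume 10%, 20% and 30%.

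**Reproducing the plan's figure.** Two-sided test, pooled variance under the null, no continuity correction:

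n per arm = [1.960 × √(2 × 0.425 × 0.575) + 0.842 × √(0.50 × 0.50 + 0.35 × 0.65)]² / 0.15² = 169.3, rounded up to 170, or 340 in total. This matches the SAP, so the 50% and 35% rates are taken as its working assumptions.

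**Size of the subset.** 195 × 0.50 = 97.5 (98) and 195 × 0.35 = 68.25 (68). The planned comparison therefore uses about 166 of 390 participants.

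**Scenario A: FLUS removes only immediate prescriptions.** The number of delayed prescriptions is the same in both arms. The planned RR reduces to 98/68 = 1.44 (0.50/0.35 = 1.43 unrounded), whatever the delayed share.

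| Assumed delayed share | Usual care, planned | +FLUS, planned | Planned RR | Pearson p | RR per randomised participant |
|---|---|---|---|---|---|
| 10% | 10/98 | 10/68 | 1.44 | 0.38 | 1.00 |
| 20% | 20/98 | 20/68 | 1.44 | 0.18 | 1.00 |
| 30% | 29/98 (29.6%) | 29/68 (42.6%) | 1.44 | 0.083 | 1.00 |

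Confidence intervals by the log method, at the 30% share:
- Planned: SE of log RR = √(1/29 − 1/98 + 1/29 − 1/68) = 0.210, so 95% CI 0.96 to 2.17.
- Delayed per randomised participant: 29/195 in each arm, SE = √(2/29 − 2/195) = 0.242, so RR 1.00 (0.62 to 1.61).
- Immediate per randomised participant, where the change actually lies: 98 − 29 = 69 and 68 − 29 = 39, so 39/195 against 69/195, RR 0.57 (0.40 to 0.79).

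None of these expected results falls below 0.05. With sampling variation (40,000 simulated trials, 195 per arm, Pearson chi-squared), the planned test gives p < 0.05 in about 14%, 25% and 40% of trials at shares of 10%, 20% and 30%. The same test per randomised participant does so in about 5%. A normal-approximation power calculation on the planned denominator agrees (13.8%, 25.2%, 40.0%).

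**Scenario B: both types fall in proportion, 30% share.** Delayed in +FLUS = 29 × 68/98 = 20.1 (20).
- Planned: 20/68 (29.4%) against 29/98 (29.6%), RR 0.99 (0.62 to 1.60).
- Per randomised participant: 20/195 (10.3%) against 29/195 (14.9%), RR 0.69 (0.40 to 1.18).
- Without rounding the two RRs are 1.00 and 0.70.

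**The case against.** The strongest reply is that the denominator is inferred. The SAP gives no formula, section 5.1 states intention to treat in general terms, and the options column of Table 1 may record how an item is coded rather than who is analysed. Satisfaction, for instance, is listed there with five levels but analysed as a dichotomy. It is true that the reading is inferred. But the change of base from participants to antibiotics between 2.2 and 2.3 is plain, and the intention-to-treat sentence gives an unprescribed participant no value on a two-level variable. If all participants were meant, the definition and the table row still need correcting.

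It can also be said that the delayed share is a legitimate quantity and that the SAP does not claim it estimates an effect per patient. That holds for the share as a description. It does not justify an RR, CI and test between arms.

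A fair caution concerns the 14%, 25% and 40%. In scenario A the conditional share really does differ between arms, so these are not inflated type I errors for that share. They show how often the planned test would signal a difference when delayed prescribing per randomised participant is unchanged.

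Finally, the counts per randomised participant can be derived from the planned 2×2 table and the planned shares. They can, but no RR or CI is planned for them.

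**Conclusion.** The concern holds. Followed as written, the SAP attaches a between-arm RR, CI and test to a subset selected by the primary outcome. At the SAP's own prescribing rates, the planned RR is about 1.43 times the RR per randomised participant (0.50/0.35) whatever the delayed share: it reads 1.44 in rounded counts when the true ratio is 1.00, and about 1.00 when the true ratio is 0.70.

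This rests on the natural reading of the denominator, the 50% and 35% rates, and two illustrative mechanisms. The delayed shares of 10% to 30% are assumed and affect only the intervals, p-values and rejection rates. The primary analysis and the sample size are untouched. The correction should be made before analysis, but it concerns one secondary outcome.

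**What to change.** In outcome 2.3 and its Table 1 row, classify every randomised participant at day 0 as none, immediate or delayed. Give the RR and 95% CI per randomised participant for delayed (yes/no) and for immediate (yes/no). Report the share of prescriptions that were delayed by arm as description, with its denominator stated and without an RR or test.

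The cost is a change of SAP wording; the data are the same.
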